#### Situational Analysis: FGD with Patients/Carers

Introduce yourself, explain the purpose of the FGD, take informed consent. Remind participants about confidentiality.

- 1. Please describe your/your dependent's current experiences of SCD care.
  - a. Probe: Where do you/your dependent receive care?
  - b. Probe: Is this care good quality? (Why or why not?)
  - c. Probe: Do you feel that you/your dependent's needs in terms of SCD management are being met? (Why or why not?)
- 2. What treatment(s) do you/your dependent receive?
  - a. Probe: Hydroxyurea? Penicillin? Blood transfusion? Pain management?
  - b. Probe: How often?
  - c. Probe: Are you given information about what these treatments do?
- 3. Do you incur any costs for SCD care?
  - a. Probe: Indirect costs (e.g. transportation, meals, accommodation)?
- 4. What is most important to you in terms of SCD care?
  - a. Probe: Being treated with respect? Open communication? The ability to ask questions?
  - b. Probe: Receiving medication?
- 5. Are there any barriers that you/your dependent face in terms of accessing SCD care? (Please explain)
- 6. Does anything make it easier for you/your dependent to access SCD care?
  - a. Probe: Outreach services?
  - b. Probe: Community-base or other non-governmental organisations?
- 7. What aspects of how SCD care is provided do you think are positive?
- 8. How would you improve SCD care?
- 9. Do you have any further comments?

Please thank the participants for their time.

#### Situational Analysis: FGD with SCD Clinicians

Introduce yourself, explain the purpose of the FGD, take informed consent. Remind participants about confidentiality.

- 1. Please describe how someone is diagnosed with SCD in your health facility/ies.
- 2. Do you feel that most patients have a timely diagnosis? (Why or why not?)
  - a. What do you feel constrains early diagnosis of SCD care?
  - b. What do you feel facilitates early diagnosis of SCD care?
- 3. Please describe how SCD is treated at your health facility/ies.
  - a. Probe: Hydroxyurea? Penicillin prophylaxis? Blood transfusion? Pain management?
- 4. What do you feel are positive aspects of the SCD care provided?
- 5. What do you feel could be strengthened in the SCD care provided?
- 6. What do you think "patient-centred" SCD care would include?
  - a. Probe: Communication with patient? Dialogue? Involvement of the patient in decision-making? Empathy?
- 7. What do you feel constrains uptake of SCD care?
- 8. What do you feel facilitates uptake of SCD?
  - a. Probe: Outreach services?
  - b. Probe: Partnerships with local organisations?

Please thank the participants for their time.

#### Situational Analysis: FGD with Community Members

Introduce yourself, explain the purpose of the FGD, take informed consent. Remind participants about confidentiality.

- 1. Please describe what you understand "sickle cell disease" to mean.
  - a. Do you think most people in this community understand what SCD is?
  - b. Do you know the difference between carrying a SCD trait versus having SCD?
- 2. Do you know anyone with (or who had) SCD?
- 3. Do you know how people get SCD?
- 4. Do you know what happens when someone has SCD?
- 5. Do you think that someone with SCD can live a normal life?
- 6. Do you know where people with SCD/their carers can access treatment?
- 7. Do you think it is challenging for people in this community to access healthcare? (Why or why not?)
  - a. Probe: Expenses?
  - b. Probe: Transportation?
- 8. When do you think people with SCD should be diagnosed?
- 9. Do you think that people with SCD face stigma in this community? (Why or why not?)
- 10. Any further comments?

Please thank the participants for their time.

#### Situational Analysis: KII with Decision-makers

Introduce yourself, explain the purpose of the interview, take informed consent. Remind participant about privacy.

- 1. Please describe your role.
- 2. What do you think is the burden of SCD in this [country/district/state]?
  - a. Probe: Are there good estimates of incidence/prevalence? From where?
  - b. Probe: Are there "pockets" where you see more SCD than others? Why?
- 3. Do you feel that SCD is a priority in this [country/district/state]? (Why or why not?)
- 4. What policies are in place that dictate clinical care for SCD?
  - a. Probe: Are these adequate?
  - b. Probe: Do you know when these were last updated?
- 5. Are there any policies in place to support community (demand-side) factors influencing SCD care? (Please describe)
  - a. Probe: Anything to support community sensitisation for SCD?
  - b. Probe: Anything to support early diagnosis of SCD?
  - c. Probe: Anything to support uptake of SCD care?
- 6. Are you aware of specific resources that are earmarked to support SCD care? (Please explain)
- 7. What are some of the biggest barriers in this [country/district/state] to providing effective SCD care?
  - a. How do you feel these might be resolved?
- 8. Are there any forthcoming changes to SCD policy/guidelines/resource allocation that you are aware of? (Please describe if so)
- 9. Any further comments?

Please thank the participant for their time.

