The decision to transfuse a patient with SCD must be taken by a trained clinician with expertise in managing patients with SCD because they need to consider the degree of anaemia relative to the patient's steady state haemoglobin concentration and overall clinical condition. In high income countries all SCD patients must have extended red cell antigen typing performed to prevent the development of antibodies after transfusion. However, such typing is not widely available in SSA. In SSA, shortages of blood and facilities able to provide a transfusion, mistrust of the health system, lack of understanding about blood donation and the transfusion process, and poor uptake of care mean that when blood is available it is mostly used in SCD for treatment of acute anaemia.

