#### Qualitative study

To explore and explain findings from the review and the survey, we will carry out additional qualitative data collection. This will involve three **focus group discussions** (FGDs) per country focussing on:

- 1. *Patients/carers* to help us to understand what SCD patients/carers need and expect from care, their perceptions of the quality of care received, their ideals for "patient-centred SCD care", and constraints they face in accessing care.
- 2. *Community members* more broadly (religious and other community members, traditional healers, other influential community members) to establish localised understanding of SCD and perceptions around community access to health facilities.

<sup>† We are planning to follow this with research into how best to support journalists to engage more effectively with SCD patients and researchers. We will also apply for separate ethics for this activity.

3. *Health facility staff* providing SCD care to establish standards of care currently in place, typical approaches in SCD care, their views on what "patient-centred SCD care" would entail, and perceptions around quality of SCD care and areas for improvement (see Appendix 1 for FGD guides).

**Key informant interviews:** 5–10 will take place with policymakers who play a role in SCD and community health decision-making in order to determine which policies guide SCD in each country, resource allocation for SCD care, and higher-level facilitators and barriers of SCD care. These key informants may include Directors of Clinical Services/Public Health and National/Zonal Blood Services and senior facility and university officials responsible for training in SCD care (e.g. Medical Directors, Deans). We will also carry out key informant interviews with representatives from community-based or national-level organisations supporting patients with SCD and carers of children living with SCD to understand their perspectives around uptake of care, common misconceptions, patient-centredness in SCD care, and facilitators and barriers of uptake and delivery of quality SCD care.

Findings from the situational analysis will by synthesised and shared with PAC and SBA teams as a springboard for discussion and to inform priority topic areas for each group.

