Please note that sample size calculations have not been made, as we are not making statistically significant inferences, but simply carrying out this survey in an exploratory way to gain insights from a broad cross-section of SCD-patients and carers of children living with SCD. At each teaching hospital (one in Abuja, one in Lusaka, one in Kumasi), there are approximately 2000–3000 SCD patients who receive care regularly throughout the year. Given our timeline, we estimate that it would therefore be plausible over a three-month period to obtain survey responses from 300 unique patients/carers. The numbers of SCD-affected persons/ carers of children living with SCD who do not receive care is unknown in all contexts, and we anticipate that it will may be much more challenging to identify these participants, however, their perspectives are incredibly important. As such, we will continue to recruit until we reach 100 unique participants, though this may need to be adjusted down if this is simply not possible within the three months allotted for this survey.

In months 15-18, each PACs team (1/facility) will be drawn from communities within the catchment area of each participating health facility. Each team will comprise SCD patient/carers and influential community members/decision-makers (which may also include traditional healers) for approximately 10 people per team. Inclusion of community members will improve the community's understanding of the challenges faced by SCD patients. Community team members will be accessed first by identifying and liaising with community-based organisations that support SCD-affected persons, who will serve as community gatekeepers in addition to providing suggestions for possible participants. Discussions with community leaders to identify prospective participants as well as snowball sampling (e.g. an identified carer may be aware of another carer in their community) will also take place. Inclusion criteria will be: aged 18 and older (unless a person living with SCD, in which case they must be at least 15 years of age); a carer of someone (alive or deceased) with SCD or someone living with SCD or a community leader or a traditional healer; must be literate; must be willing to consent. Each prospective participant will be approached by the study team and given study materials (the participant information sheet). They will be given at least one week to decide their participation.

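### The decision-maker interview guide has no direct question on facilitators, although Section 3.3 makes them a purpose of those interviews

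*Protocol*

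**What the plan says.** Protocol Section 3.3, Qualitative study, gives the purpose of the key informant interviews with policymakers: to find out which policies guide care, and to learn about "resource allocation for SCD care, and higher-level facilitators and barriers of SCD care". Facilitators and barriers are named together, on an equal footing. On who may be interviewed it says: "These key informants may include Directors of Clinical Services/Public Health and National/Zonal Blood Services and senior facility and university officials responsible for training".

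Appendix 1 (Situational Analysis: KII with Decision-makers) holds the guide. Its nine items cover the informant's role, burden, priority, clinical policies, community-side policies, earmarked resources, barriers, forthcoming changes and further comments. Item 7 is the barrier question: "What are some of the biggest barriers in this [country/district/state] to providing effective SCD care". Its follow-up, 7a, asks how the barriers might be resolved.

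Table 1 plans 5–10 key informant interviews per country in three countries.

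**The concern.** A guide should have at least one question for each thing that its interviews are meant to find out. Here three of the four stated topics have one and the fourth, facilitators, does not.

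The answers go into the initial programme theory, which sets out what in the context is likely to drive patient-centred, evidence-based care. If senior informants are asked what hinders care but not what has helped it, their contribution leans towards obstacles, and enabling conditions at policy level appear only when someone volunteers them. The Timeline puts the qualitative study in months 12–15 and the initial theory in month 15. The first realist-evaluation round is in month 18, so later stakeholder interviews cannot supply the missing material for that first version.

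**Working it through.** No formula applies, and the plan gives no figure to reproduce. The check sets the stated purpose beside the guide, item by item, and then beside the other Phase 1 guides.

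**Step 1. Purpose against items (decision-maker guide).**

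| Purpose in Section 3.3 | Items that address it | Asked directly? |
|---|---|---|
| Policies | 4 (clinical policies, adequacy, last update), 5 (community side), 8 (forthcoming changes) | Yes |
| Resource allocation | 6 (earmarked resources), 8 | Yes |
| Higher-level barriers | 7 | Yes |
| Higher-level facilitators | none | No |

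The other items are 1 (role), 2 (burden), 3 (priority) and 9 (further comments). Direct facilitator questions: 0 of 9.

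**Step 2. Items that come near.**
- Item 5, with its three probes, asks whether supportive policies exist for sensitisation, early diagnosis and uptake. It does not ask whether they have helped.
- Item 6 asks whether resources are set aside.
- Item 7a asks for solutions to barriers, which are things not yet done.
- Item 8 asks about changes still to come.

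Each reaches an enabling factor from the side. None asks what has made care easier or better.

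**Step 3. The other Phase 1 guides.**
- Patients/carers FGD: item 6 asks whether anything makes access easier.
- Clinicians FGD: items 2b and 8 ask what facilitates early diagnosis and uptake.
- Organisation representatives: separate questions on what might facilitate early diagnosis and access, each paired with a question on constraints.
- Community members FGD: no facilitator question, but Section 3.3 gives that session a different purpose (local understanding of the disease and perceptions of access).

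So the guides for patients/carers, clinicians and organisations ask about facilitators, while the guide whose stated purpose includes higher-level facilitators does not.

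**Step 4. Blood supply and training.** Items in the decision-maker guide that mention either: 0 of 9. Section 3.3 lists officials from both fields as possible informants, and Section 1.1 names "shortages of blood and facilities able to provide a transfusion" among the constraints in sub-Saharan Africa. Item 7 is open, however, and follows a question on the informant's role, so an official from either field can raise these topics there. They are unprompted, not excluded.

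**Step 5. Size.** 5 × 3 = 15 and 10 × 3 = 30 interviews. This is an upper bound for the decision-maker guide: Section 3.5 counts organisation representatives as key informants and Table 1 has a single row for all of them. Any of the 15–30 who are organisation representatives use the other guide, which does ask about facilitators.

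**The case against.** The best defence is that these are semi-structured interviews with senior people. Items 5, 6, 7a and 8 give several openings to talk about what supports care, and a competent interviewer will follow them up. Section 5.7 also commits the team to piloting all instruments, partly to find missing questions, and facilitators are asked about in three other guides.

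Much of this stands, and it is why the point is small. It does not remove the mismatch. The indirect items concern what exists, what might be done or what is coming, and not what has worked. Facilitators seen by patients, clinicians and organisations are not the higher-level ones that these interviews were given to find. Piloting might catch the gap, but it can be seen now by reading the guide against its purpose.

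On blood and training the defence is stronger. Section 3.3 promises neither as an interview topic, and its wording on these officials is permissive. Phase 2 also plans interviews for which blood-service staff are given as an example, and blood-service stakeholders are to be invited to learning collaboratives. Probes on these topics would therefore be an improvement, and their absence breaks no commitment.

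**Conclusion.** The point holds as a minor mismatch between instrument and purpose: one of four stated topics of the decision-maker interviews has no direct question, in at most 15–30 interviews. This assumes that the guide is used as printed. Section 3.3 expressly calls only the survey tools drafts.

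A reader might infer three stronger things, and the documents support none of them.

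- *That part of research question i goes unasked.* That question asks why proven interventions are not widely used. It does not mention facilitators, blood or training, and item 7 puts it openly to decision-makers.
- *That heads of blood services and training are certain to be interviewed and then not asked about their fields.* Section 3.3 lists them only as possible informants.
- *That the clinician guide leaves audit teams unable to tell a missing standard from an unmet one.* Section 3.3 says the staff session is for those "providing SCD care to establish standards of care currently in place", while item 3 of that guide asks "Please describe how SCD is treated at your health facility/ies", which is a question about practice. But the scoping review collates current guidelines in each country, item 4 of the decision-maker guide asks which policies govern clinical care, and clinician item 3a probes hydroxyurea, penicillin and transfusion. Under Section 2.2 each audit team also identifies its own standard and measures performance against it.

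**What to change.** After item 7 of the decision-maker guide, add one question: *What has helped SCD care in this [country/district/state]?*

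Optionally, add short probes under item 7, used according to the informant's role: one on the availability of blood for SCD patients (blood-service officials) and one on training in SCD care (training officials).

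The cost is a few minutes per interview. No new participants and no change of design are needed, and the wording can be tested in the piloting already planned under Section 5.7.

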#### Situational Analysis: KII with SCD Community-based Organisation/Nongovernmental Organisation Representatives

# Introduce yourself, explain the purpose of the interview, take informed consent. Remind participant about privacy.

- 1. Please describe your role.
- 2. Please describe the activities of your organisation with respect to SCD.
  - a. Probe: Community sensitisation?
  - b. Probe: Support accessing care?
  - c. Probe: Support in provision of care?
- 3. What do you think is the burden of SCD in this community?
  - a. Probe: Are there good estimates of incidence/prevalence? From where?
  - b. Probe: Are there "pockets" where you see more SCD than others? Why?
- 4. Do you think there is a problem of SCD stigma in this community? (Please explain)
- 5. What are some common community misconceptions about SCD, if any?
- a. Probe: Does your organisation do anything to redress these misconceptions?6. What do you think patients with SCD/their carers want from SCD care?
  - a. Probe: Do you think that current care available meets those expectations? (Why or why not?)
- 7. What do you feel "patient-centred SCD care" would look like?
  - a. Probe: Greater empathy? More communication and information provided? Patient involvement in decision-making?
- 8. What do you think constrains early diagnosis of SCD in this community?
- What do you think might facilitate early diagnosis of SCD in this community?
   a. Probe: Is your organisation doing anything to support this?
- 10. What do you tin constrains access to SCD care in this community?
- 11. What do you think might facilitate access to SCD care in this community?
  - a. Probe: Is your organisation doing anything to support this?
- 12. Any further comments?

Please thank the participant for their time.

## Realist Evaluation: Observation Template

| Date   |  |
|--|--|
| Location   |  |
| Activity   |  |
| Attendees  |  |
|  |  |
|  |  |
| Discussion points
(e.g. challenges/problems
arising; solutions and
implementation; decisions
made; information
discussed) |  |
|  |  |
|  |  |
| Observations about
team/group dynamics  |  |
| Other observations   |  |
|  |  |

# Realist Evaluation: Reflective Diary Template

| Date  |  |
|---|--|
| Activity/ies  |  |
| Reflections
(e.g. Positive points,
challenges, questions
arising, reflections on
context, etc.) |  |
| Points to discuss with
supervisor  |  |

# Realist Evaluation: FGD with PAC Team Members

Introduce yourself, explain the purpose of the FGD, take informed consent. Remind participants about confidentiality.

- 1. Please describe the role of this team.
- 2. Please describe your team's activities over the past [months/year]
  - a. Probe: problems established?
  - b. Probe: Actions generated?
  - c. Probe: Anything implemented?
  - d. Probe: Success of what was implemented? (Please explain how you knew it was successful or not)
- 3. What do you feel is working well within this team?
- 4. What are some of the challenges that this team is facing?
- 5. Do you think that this team is making an impact? (Please explain)
- 6. Do you feel confident that you can introduce positive change in this community? (Please explain)
- 7. Please describe what has happened during learning collaboratives.
- 8. Is it useful to come together with other community teams in learning collaboratives? (Please explain)
- 9. Have you found it useful to work with the clinical teams during learning collaboratives? (Please explain)
  - a. What are some challenges to working with the clinical teams?
  - b. What are some advantages to working with the clinical teams?
- 10. Are there any further skills or knowledge that you feel you need, as a team, to work more effectively?
- 11. Any further comments?

Please thank the participants for their time.

# Realist Evaluation: FGD with SBA Team Members

Introduce yourself, explain the purpose of the FGD, take informed consent. Remind participants about confidentiality.

- 1. Please describe the role of this team.
- 2. Please describe your team's activities over the past [months/year]
  - a. Probe: problems established?
  - b. Probe: Actions generated?
  - c. Probe: Anything implemented?
  - d. Probe: Success of what was implemented? (Please explain how you knew it was successful or not)
- 3. What do you feel is working well within this team?
- 4. What are some of the challenges that this team is facing?
- 5. Do you think that this team is making an impact? (Please explain)
- 6. Do you feel confident that you can introduce positive change in this health facility? (Please explain)
- 7. Please describe what has happened during learning collaboratives.
- 8. Is it useful to come together with other clinical teams in learning collaboratives? (Please explain)
- 9. Have you found it useful to work with the community teams during learning collaboratives? (Please explain)
  - a. What are some challenges to working with the community teams?
  - b. What are some advantages to working with the community teams?
- 10. Are there any further skills or knowledge that you feel you need, as a team, to work more effectively?
- 11. Any further comments?

Please thank the participants for their time.

# Realist Evaluation: In-depth Interview with SCD Stakeholders

Introduce yourself, explain the purpose of the interview, take informed consent. Remind participant about privacy.

- 1. Please describe your role.
- 2. Have you heard of the PACTS intervention? [May need to briefly describe and re-ask if they are not familiar with the acronym]
  - a. If yes: Can you briefly describe what the intervention involves?
  - b. If yes: Do you think the intervention has resulted in any changes in this [community/health facility]? (Please explain)
- 3. In the past [months/year], have you noticed any changes in [community perception/diagnosis/uptake] of SCD? Please explain.
  - a. Probe: Why do you think those changes are occurring?
- 4. In the past [months/year], have you noticed any changes in SCD care? Please explain.
  - a. Probe: Why do you think those changes are occurring?
- 5. Are there any other interventions or organisations active in SCD in this [community/health facility]?
  - a. Probe: Can you describe what they do?
- 6. What do you feel is needed in this [community/health facility to support better [uptake/provision] of SCD care? (Please explain)
- 7. Any further comments?

Please thank the participant for their time.

